#### ***Atrial Arrhythmia (AA) Recurrence***

The rate limiting factor in the required sample size is AA recurrence (atrial fibrillation, atrial flutter, atrial tachycardia). AA recurrence is defined as a one instance, continuous >30 second strip reading on either 12-lead ECG, Holter monitor or study devices (including during the blanking period)

AA recurrence will be based on the following assumptions:

- 50% of patients in the control group will have AA recurrence in 1-year, post-ablation (including during the blanking period) and,
- the relative reduction of AF recurrence will be by 33% in the dronedarone group compared to the control group and,
- 20% of subjects could be lost during the follow-up periods and,
- 2-sided  $\alpha=0.05$ .

The EDORA trial will have a total of 330 patients participating, thus, 165 in each trial arm. Therefore, a calculated total of 138 AF recurrences will have 86% power to detect the group differences.

The study will be defined as successful if the hypotheses for both co-primary endpoints are positive, i.e., rejecting the null hypothesis. Therefore, in terms of overall type I error of the study, the sample size calculation does not need to adjust for the multiplicity. However, the type II error, i.e., the power for each individual test needs to be adjusted in this case to achieve the overall power of the study. For the endpoint of atrial fibrosis progression, given that 330 patients will be recruited, we have almost 100% power to detect the expected difference. For AF recurrence, the study will have at least 85% power. Therefore, for the two co-primary endpoints, the study will have at least 85% overall power for a positive outcome, i.e., the study is powered to detect the difference in both atrial fibrosis progression and AF recurrence between the two arms.

Most studies evaluating the effects of AAD after ablation started their monitoring after the 3-month blanking period. Our trial will start assessing for the primary endpoint of AF recurrence on the day of discharge, and so we expect a significantly higher event rate. A few recent studies reporting recurrence data during the first three months after ablation such as, the AMIO-CAT study showed a 53% AF recurrence rate after ablation in a placebo group and AF recurrence at 6 months was 48%. In the EAST-AF study, randomizing paroxysmal and persistent AF patients to short term AAD use vs control, the rate

Page 34 of 49

Version 4.0:  
Revision Date: April 27th, 2022

Copyright© April 2022 Tulane University School of Medicine, Academic Research Organization on behalf of the Principal Investigator.  
All rights reserved.

TULANE UNIVERSITY  
Academic Research Organization

of AF recurrence 3 months after ablation was 48% and 30% at 9 months follow-up. Recurrent 30-day monitoring using an ECG monitoring device in our study is expected to provide a higher event rate than observed in previous AAD vs control studies, in which monitoring was performed at a limited number of follow-up visits.

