### **A. Sample Size Estimation**

#### ***Atrial Fibrosis Progression***

Based on the assumption that the mean progression of fibrosis in the control group is 10%, the SD for the progression of fibrosis is 1.59. Predicting a 20% dropout rate, 86 randomized patients will provide >99% power with a 2-sided  $\alpha= 0.05$  to detect a reduction of 20% in fibrosis progression between dronedarone and the control arm. Given that an estimated 330 patients will be recruited, the study will have approximately 100% power to detect the group difference in atrial fibrosis progression.

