## C. Analysis of the co-primary endpoints

### *Analysis of AF Recurrence*

Time-to-event-analysis will be conducted for AF recurrence. Patients with unobserved AF events during the study trial due to loss-of-follow-up/death or termination of the study will be treated as censored and the time to first AF recurrence will be treated as the outcome. Cumulative AF rates will be calculated by intervention conditions using the Kaplan-Meier (KM) method and compared using the log-rank test. Stratified KM curves will also be performed by Utah Stages at baseline (separate strata for Utah stages I - II, and III - IV) to investigate if the treatment effects vary across different stages. Cox proportional hazards models will be used to assess the intervention effects on the time to AF recurrence after discharge from the procedure. The proportional hazards assumption will be tested by means of graphical methods and statistical tests of lack of fit.

Due to the nature of the randomization in the study design, it is expected that the demographic characteristics and other important clinical factors will be balanced between the two groups. However, in addition to the primary predictor and the intervention condition, potential confounders will also be included in the model.

Due to the clustering effects at a physician level, we will include random effects of the physician in the model. We will also further investigate if the intervention effects are similar across the stages after controlling potential confounding effects by including the interaction of the intervention and the Utah stage in the models. In all the models, the estimated hazard ratio between the treatment and control groups with its 95% confidence interval will be provided.

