### *Analysis of LA Fibrosis Progression*

The primary outcome variable will be changes in the percentage of fibrosis from baseline, 3- and 12-months via CMR assessments in patients randomized to receive dronedarone vs. placebo.

We will apply models for longitudinal data to analyze the LA fibrosis progression over the follow-up period. The two most popular approaches for longitudinal data are the Linear Mixed-effects Model approach (LMM) and Generalized Estimating Equations (GEE). The LMM requires parametric assumption such as, normality on the random effects and model errors, and it is more powerful when the assumptions are met, but vulnerable to departures from the assumed distributions. GEE provides robust

estimates because it does not require any distribution assumption. Therefore, we will first investigate the distribution of the outcome, and if the distribution assumption is reasonable, we will use LMM model, otherwise, we will use GEE approach. Due to the clustering effect at a physician level, we will use random effects in LMM or working correlation in GEE model to account for the correlations. In all the models, the primary predictor is the intervention condition. We will also consider controlling other potential confounders if the data exhibits any. The intervention effect is assessed by the estimated coefficient of the primary predictor. The coefficient with right direction and a p value  $<0.05$  indicates there is a significant intervention effect.

Per standard principles, the primary analyses will be done on an intention to treat basis (ITT), treating all randomized patients with available outcome data regardless of compliance. A Robustness Analysis will include a per protocol analysis, where only those patients who actually received their assigned treatment (e.g., those who received dronedarone per the dosing protocol) will be analyzed. In terms of missing data, the survival analysis approach to the AF recurrence outcome will censor any patients who drop out of the study without AF recurrence at the time of their last known contact. While we would propose such patients to have their first documented recurrence date counted as their failure date, alternative analysis approaches for the analysis of interval-censored data will also be considered for robustness.

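### The 138 recurrences and 86% power for the AA co-primary endpoint are complete 1-year follow-up figures; the 20% loss listed among the inputs is not applied

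*Combined protocol and SAP*

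**What the plan says.** In part A of the statistical section, under Atrial Arrhythmia (AA) Recurrence, the plan calls this endpoint the rate-limiting one for sample size. It assumes 50% control recurrence within 1 year (blanking period included), a 33% relative reduction on dronedarone, two-sided alpha 0.05, and that "20% of subjects could be lost during the follow-up periods". With 165 patients per arm it concludes that "a calculated total of 138 AF recurrences will have 86% power to detect the group differences".

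The result is carried forward twice: "For AF recurrence, the study will have at least 85% power", and, because both co-primary endpoints must succeed, "the study will have at least 85% overall power for a positive outcome".

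Four other places bear on this:

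- Study Participant Replacement says that patients who discontinue are not replaced.
- The missing-data text under Analysis of LA Fibrosis Progression says that the survival analysis "will censor any patients who drop out of the study without AF recurrence at the time of their last known contact".
- The arms are "compared using the log-rank test" (Analysis of AF Recurrence).
- Study Duration and Close Out gives 13 months of follow-up, whereas the 50% recurrence rate is stated for 1 year.

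**The concern.** The conclusion is presented as following from the four listed inputs, but the arithmetic uses only three of them. The other co-primary endpoint is handled differently: "Predicting a 20% dropout rate, 86 randomized patients will provide >99% power" ties the loss to the number randomised, and that claim holds once loss is applied. A reader will assume that the same was done for AA recurrence.

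Fibrosis power is put at almost 100%, so the chance of a positive trial is essentially the AA power. By Freedman's formula the complete-follow-up figure exceeds 85% by only about 1 point. Whether that margin survives the plan's own loss assumption is the question left open.

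**Working it through.** **Inputs (AA Recurrence section).** Control rate 0.50; dronedarone rate 0.50 x 0.67 = 0.335; 165 per arm; two-sided alpha 0.05; loss 20%. Under proportional hazards, HR = ln(0.665)/ln(0.5) = 0.589.

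**Reproducing the plan's figures, no loss**

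- Events: 165 x 0.50 + 165 x 0.335 = 82.5 + 55.3 = 137.8, which rounds to 138.
- Freedman power: Φ(√137.8 x (1 − 0.589)/(1 + 0.589) − 1.96) = Φ(1.08) = 86.0%.
- Schoenfeld power: Φ(√137.8/2 x |ln 0.589| − 1.96) = Φ(1.15) = 87.5%.
- Two proportions, 165 complete patients per arm: 86.3%.
- In reverse: 138/0.835 = 165.3 per arm, so N = 330 contains no inflation for loss either.

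Both stated figures are thus recovered with complete follow-up.

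**Adding 20% loss.** For each arm, expected events = 165 x ∫ f(t) G(t) dt, where f is the density of time to recurrence and G(t) is the probability of still being followed at t. At 1 year, any G below 1 gives fewer than 137.8 events. Two cases by hand:

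- All loss at the start: 0.8 x 137.8 = 110.2 events.
- Constant recurrence hazard λ with exponential loss, rate μ = −ln 0.8 = 0.223 per year. The proportion with an observed event is λ/(λ+μ) x (1 − e^−(λ+μ)). Control (λ = 0.693): 0.756 x 0.600 = 0.454. Dronedarone (λ = 0.408): 0.646 x 0.468 = 0.303. Events: 74.9 + 49.9 = 124.8.

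The other rows come from the same integral. "Early" in the table means 96% of control recurrences in the first 90 days. This is an assumption: the cited 3-month rate of 48% (the study in which the rate "of AF recurrence 3 months after ablation was 48% and 30% at 9 months follow-up") divided by the assumed 50% at 1 year. All loss timings are also assumptions.

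| Loss (20% in total) | Recurrence | Horizon | Events | Freedman % | Schoenfeld % |
|---|---|---|---|---|---|
| none | either | 1 year | 137.8 | 86.0 | 87.5 |
| all at start | either | 1 year | 110.2 | 77.6 | 79.5 |
| spread (exponential) | constant hazard | 1 year | 124.8 | 82.5 | 84.2 |
| spread | early | 1 year | 133.8 | 85.0 | 86.5 |
| uniform from day 90 | early | 1 year | 137.2 | 85.8 | 87.4 |
| spread | constant hazard | day 395 | 132.3 | 84.6 | 86.2 |
| spread | early | day 395 | 134.6 | 85.2 | 86.7 |
| uniform from day 90 | early | day 395 | 137.8 | 86.0 | 87.5 |
| only after day 270 | constant hazard | day 395 | 142.4 | 87.1 | 88.5 |

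Simulated log-rank tests (40,000 runs each) gave 87.1% with no loss at 1 year. For the four spread-loss rows, in table order, they gave 83.6%, 86.2%, 85.9% and 86.4%.

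**Events needed for 85% power:** 134 (Freedman) or 128 (Schoenfeld).

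**Fibrosis comparison:** 86 x 0.8/2 = 34 per arm; difference 20% of 10 = 2; SD 1.59; power 99.9%. Here the stated power survives the loss.

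**The case against.** The best defence has four parts.

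1. *Loss timing is unstated, so no shortfall is proved.* This stands as to size. An overstatement of 3 to 13 events, or about 1 to 3.5 points by Freedman, would follow only from loss spread exponentially from day 0. Loss at the start does more harm, and late loss does almost none. It does not rescue the derivation: at 1 year every loss pattern gives fewer than 137.8 events. The cases that reach 138 need a longer horizon than the one for which the 50% rate is stated.

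2. *Recurrences come early.* This is fair. Monitoring starts at discharge, the blanking period counts, and the plan cites a high 3-month rate. Early recurrence is closer to what the plan expects than a constant hazard. With spread loss, the Freedman power then falls by only about 1 point, and the simulated log-rank power is 86.2% at 1 year.

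3. *138 events do give 86% power.* True, but the plan presents 138 as the count its inputs produce. Follow-up is fixed at 13 months, and nothing extends it until 138 events have accrued.

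4. *Other events count too.* Antiarrhythmic drug initiation without a positive ECG, and repeat ablation without ECG proof, also count as recurrence. They could add events, but the plan gives no number, and they cannot explain an exact match to 165 x 0.835.

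It might also be said that the 50% is already net of loss. The plan does not say so, and the separate 20% line would then have no role.

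**Conclusion.** The concern holds in this form: 138 events and 86% power are complete 1-year follow-up figures, although the plan lists 20% loss among the inputs from which it derives them. This part is exact and does not depend on any assumed timing.

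The size of the effect is undetermined. In the 1-year scenarios above, 20% loss gives about 110 to 137 events, with Freedman power of about 78% to 86%. To day 395, spread loss gives about 132 to 135 events (Freedman 84.6 to 85.2%, Schoenfeld 86.2 to 86.7%), and back-loaded loss can reach or exceed 138 events and 86%. These figures assume proportional hazards at HR 0.589, loss independent of recurrence, and the loss and event timings shown.

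A reader might infer that the statements of at least 85% power are false, or that the trial is underpowered and needs more patients. The documents do not support that. Power stays at or above 85% in several plausible loss-inclusive cases. Among the spread-loss cases it falls below 85% by both formulas and by simulation only with a constant hazard stopped at 1 year, which is not the pattern the plan expects. What can be said is that the only calculation behind those statements leaves out a listed input and has about a 1-point margin by Freedman.

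**What to change.** In the AA Recurrence section:

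- Label 138 events and 86% power as complete 1-year follow-up figures, and name the formula and hazard ratio.
- Add the expected events and power after 20% loss, stating the assumed loss timing, event timing, horizon (1 year or 13 months) and formula. These should be the sponsor's own assumptions; the scenarios above are illustrations, not text to adopt.
- Restate the AF-recurrence power and the overall co-primary power to match the chosen scenario.

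No change to the sample size, the analysis or the decision rule is asked for. The cost is protocol wording, and the stated power may become slightly less favourable.

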## B. General Considerations for Data Analysis

Data analysis will be conducted to address the research questions. All statistical tests will be two-sided with a  $p \leq 0.05$ . Descriptive statistics such as, mean (SD) for continuous variables and frequency (%) for categorical variables will be provided for baseline information. The simple t-test/Wilcoxon rank sum test or chi-square tests will be applied to compare the demographic information and the baseline clinical measurements between the intervention and control groups to assess if randomization is successful at each site. Any imbalanced information will be included in the regression models to account for potential confounding variables in assessing treatment effects. All primary efficacy analysis will be performed in an intent-to-treat (ITT) manner.

## C. Analysis of the co-primary endpoints

### *Analysis of AF Recurrence*

Time-to-event-analysis will be conducted for AF recurrence. Patients with unobserved AF events during the study trial due to loss-of-follow-up/death or termination of the study will be treated as censored and the time to first AF recurrence will be treated as the outcome. Cumulative AF rates will be calculated by intervention conditions using the Kaplan-Meier (KM) method and compared using the log-rank test. Stratified KM curves will also be performed by Utah Stages at baseline (separate strata for Utah stages I - II, and III - IV) to investigate if the treatment effects vary across different stages. Cox proportional hazards models will be used to assess the intervention effects on the time to AF recurrence after discharge from the procedure. The proportional hazards assumption will be tested by means of graphical methods and statistical tests of lack of fit.

Due to the nature of the randomization in the study design, it is expected that the demographic characteristics and other important clinical factors will be balanced between the two groups. However, in addition to the primary predictor and the intervention condition, potential confounders will also be included in the model.

Due to the clustering effects at a physician level, we will include random effects of the physician in the model. We will also further investigate if the intervention effects are similar across the stages after controlling potential confounding effects by including the interaction of the intervention and the Utah stage in the models. In all the models, the estimated hazard ratio between the treatment and control groups with its 95% confidence interval will be provided.

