## **Study Design**

---

EDORA is a multicenter, prospective, phase IV, randomized, and single-blinded clinical trial.

Patients with AF undergoing ablation will be stratified by age (>65 years and <65 years) and type of atrial fibrillation (paroxysmal and persistent). Upon stratification and ablation, they will be randomized to one of two trial groups. They will either receive dronedarone (i.e. Multaq®) 400mg BID (treatment group) or placebo (control group). The control group will be started on placebo and physicians will be advised to limit the initiation of AADs to essential cases only, avoiding amiodarone and dronedarone.

Each patient will receive a pre-ablation CMR scan to assess the extent of atrial fibrosis present, followed by scans at 3 and 12-month post-ablation. QoL changes will be evaluated from baseline and again at 3 months and 12-months via the AF Effect on QualiTy of life (AFEQT) questionnaire form. frequency, duration, and severity of an AF episode, if present will be evaluated from baseline and again at 3 months and 12-months via the Atrial Fibrillation Severity Scale (AFSS) questionnaire form.

Patients will be followed post-ablation for AA recurrence (atrial fibrillation, atrial flutter, or atrial tachycardia) and will receive continuous ECG monitoring via a 30-day ECG wearable monitoring device starting at discharge, then again at 3, 6, 9- and 12-months post-ablation. Patients will also be encouraged to use any personal devices that provide ECG readings (e.g. smartwatch, etc.) in between the study timepoints and to share this data with the corresponding research team.

Phone calls or study visits will be scheduled at the study participants' 6- and 9-month mark to assess for medication compliance, changes to their medical histories, medication history, and adverse event

Page 11 of 49

Version 4.0:  
Revision Date: April 27th, 2022

Copyright© April 2022 Tulane University School of Medicine, Academic Research Organization on behalf of the Principal Investigator.  
All rights reserved.

TULANE UNIVERSITY  
Academic Research Organization

reporting as well as to assess that all study devices are working accordingly. Evaluation as to whether a patient has reached any trial endpoints will also be analyzed at this time.

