### *Randomization*

Patients who meet the eligibility criteria will be randomly assigned in a 1:1 ratio (i.e. 50/50 chance of being assigned to either study arm). An Interactive Web Response System (IWRS) randomization software program will be used to assign each study participant to a study arm. Before randomization occurs, each study participant will be stratified by age (i.e. <65 years old and  $\geq$ 65 years old) and AF type (i.e. persistent and paroxysmal). Once randomization occurs, each study participant will also be assigned a participant ID number.

Randomization will occur after cardiac ablation for two major reasons. First, we want to make sure that each enrolled participant has recovered well from the procedure prior to randomization. Secondly, site investigators may desire to perform more lesions during ablation if they are aware of how the study participant was assigned (e.g. unconscious bias). Therefore, to minimize bias and to maximize balance across groups, study participants will be randomized after cardiac ablation.

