All CMR images will be uploaded to Marrek, Inc., (Salt Lake City, UT) Merisight portal as they arrive from each clinical trial site. If the imaging specialist believes the baseline image does not meet quality standards, they will not be further processed. Therefore, the patient will be excluded from the EDORA trial. CMR scans will be uploaded onto the Merisight portal. Any reports in addition to the CMR scanned images will help to aid in Marrek's calculations and analysis.

Marrek, Inc., will analyze and process the images, verifying that the patient has a proportion of atrial fibrosis (not limited to advanced stage fibrosis). Utah Stages 1-4 will be used to classify patients based on the percentage of fibrosis. Access to Merisight will also be granted to additional analysts who will separately determine LA and LV function and strain and aid in MRI sequencing.

A final report from Marrek Inc. will be uploaded onto Merisight's portal and uploaded onto DACIMA. All CMR scans will maintain identifying information to allow trial sites to verify that returned reports match the patients submitted identified information.

Baseline, 3 months, and 1-year CMR scans for 330 study participants will be pulled from Phillips IntelliSpace Picture Archiving and Communication System (PACS) and stored on DACIMA. All segmentations and images will also be stored on our encrypted server.

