### *Stratification, Randomization and Blinding*

After cardiac ablation, trial staff will stratify each participant by age (< or  $\geq$  65 years old) and type of AF (persistent or paroxysmal). After stratification, study participants will be randomized using a web-based randomization service. Other confounding variables will be adjusted for primary outcome's analysis, including UTAH fibrosis staging. As this is a single-blind trial, only patients will be blinded to the assigned treatment arm.

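### Age group and AF type stratify the randomisation but appear in no primary analysis model; covariates are left to an imbalance rule and to unnamed confounders

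*Combined protocol and SAP*

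**What the plan says.** **Design.** The Randomization section states that before allocation "each study participant will be stratified by age", cut at below 65 against 65 and over, and also by AF type. Stratification, Randomization and Blinding repeats both factors and continues: "Other confounding variables will be adjusted for primary outcome's analysis, including UTAH fibrosis staging". Study Design words the age cut differently: patients "will be stratified by age (>65 years and <65 years) and type of atrial fibrillation". A patient aged exactly 65 falls in neither of those groups.

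**Analysis.** The covariate rules are spread over several parts of the statistical section.

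- B. General Considerations: the arms are compared on baseline variables by t-test, Wilcoxon or chi-square test, to judge whether randomisation worked at each site. Then: "Any imbalanced information will be included in the regression models to account for potential confounding variables in assessing treatment effects".
- C, Analysis of AF Recurrence: "Cumulative AF rates will be calculated by intervention conditions using the Kaplan-Meier (KM) method and compared using the log-rank test". No strata are named for that test. For the Cox model: "However, in addition to the primary predictor and the intervention condition, potential confounders will also be included in the model". A physician random effect is included. Utah stage enters through separate Kaplan-Meier curves ("separate strata for Utah stages I - II, and III - IV") and through a treatment interaction examined as a further step.
- C, Analysis of LA Fibrosis Progression: adjustment for other confounders is to be considered if the data show any. Factors found to be associated with missingness are to be added to the mixed model.
- Success rule, end of C: the treatment coefficients for both co-primary endpoints must be favourable with p below 0.05.

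The CMR Protocol section says "Utah Stages 1-4 will be used to classify patients based on the percentage of fibrosis". No section says how Utah stage would be coded as a covariate.

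**The concern.** The trial is declared positive on two model coefficients, so those models should be fixed in advance and should reflect how patients were randomised. As written, the two factors the design treated as most important are not placed in any model. The covariates that do enter depend on baseline tests, on an unnamed list, or on what the data show. The Blinding section allows investigators and data analysts access to treatment arms when required, which makes covariates chosen after seeing data harder to defend. At stake are some power for arrhythmia recurrence and the clarity of the deciding analysis.

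**Working it through.** **1. The plan's own figure.** Inputs from A. Sample Size Estimation: 165 per arm, 50% control recurrence, 33% relative reduction, two-sided 0.05.

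- Treated risk = 0.50 × (1 − 0.33) = 0.335.
- Hazard ratio = ln(0.665)/ln(0.50) = 0.589.
- Events = 165 × (0.50 + 0.335) = 137.8, so 138.
- Freedman power = Φ(√138 × (1 − 0.589)/(1 + 0.589) − 1.96) = 86.0%. Schoenfeld gives 87.6%.

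The stated 86% reproduces. It uses no stratification factor, so this point does not change it.

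**2. Would the imbalance rule bring the strata in?** Simulated trials had 330 patients, equal splits and permuted blocks of 4 within the four strata (splits and block size assumed).

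- Pooled chi-square at 0.05 on age group and AF type: flagged in 0 of 72,000 trials. A pooled t-test on continuous age flagged 0.1% to 0.3%.
- The same chi-square run within each site: at least one site flagged in about 25% of trials with 5 sites, rising to about 86% with 20. The documents give no number of sites. Fisher's exact test gives 17% to 55%.

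The split arises because blocks within strata force balance over the whole trial but not within a site. Whether the strata enter the model therefore depends on how General Considerations is read.

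**3. What omission costs for arrhythmia recurrence.** The comparison is between Cox models that all contain Utah stage (I-II against III-IV), without and with age group and AF type. Event times are exponential over one year, calibrated to 50% and 33.5% risk. The Utah hazard ratio is 1.06^10 = 1.79, from the 6% per 1% fibrosis in Background over an assumed 10-point difference. The documents give no hazard ratios for age or AF type, so a range is assumed. There were 8,000 trials per setting; simulation error is about 0.4 points for power and 0.2 for type I error. Type I error was run with 20% dropout.

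| Assumed HR (AF type, age) | Power without / with, no dropout | Gain, 20% dropout | Two-sided type I error without / with |
|---|---|---|---|
| 1.0, 1.0 | 88.4% / 88.5% | 0.1 points | 5.2% / 5.2% |
| 2.0, 1.2 | 88.8% / 90.3% | 1.5 points | 4.5% / 5.0% |
| 2.5, 1.5 | 89.8% / 92.0% | 2.7 points | 4.0% / 5.2% |

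With a physician random effect in every model (20 physicians, SD 0.3 on the log hazard, both assumed), the gains are about 0, 1.1 and 2.0 points. Unequal splits (35% persistent, 55% aged 65 or over, 40% Utah III-IV, all assumed) at hazard ratios 2.5 and 1.5 give 90.3% against 92.6%.

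A log-rank test with no covariates shows the same pattern. Its loss reaches 5.5 points (82.7% unstratified, 88.2% stratified) only at the strongest assumption tried: AF type 3.0, age 2.0. Type I error there is 2.8% against 5.1%.

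**4. Room for choice among models.** Four models were compared: Utah stage alone, with AF type, with age, and with both. Under the planned effect without dropout they disagree on a favourable p below 0.05 in 0.8%, 2.6% and 3.3% of trials, in the order of the table. Always taking the smallest favourable p gives a one-sided error of 2.6%, 3.2% and 3.0% against 2.5%.

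**Not measured:** the unnamed confounders, and any effect on the fibrosis endpoint.

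**The case against.** The best defence is the sentence on other confounders in Stratification, Randomization and Blinding. It directly follows the description of the two strata, so the natural reading is that age and AF type are adjusted for as well, with Utah stage added. That is plausible as intent. It does not settle the matter: the sentence names only Utah stage, gives no coding, and is not repeated where the models are described.

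A second defence is that the consequences are small, every stratum hazard ratio is assumed, and the wider source of choice, the unnamed confounders, is unmeasured. This stands, and it limits the point to a pre-specification improvement.

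Third, the four Utah stages in CMR Protocol and the two groups in the recurrence analysis do not conflict: one classifies images, the other groups survival curves. The gap is only the missing covariate coding. Likewise, the age wording in Study Design looks like a slip, since both sections that describe the randomisation step agree.

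Two stronger readings are tempting. A reader might infer that ignoring the strata inflates the false-positive rate; the calculation shows the opposite, because stratified randomisation removes variation that the unadjusted standard error still counts. A reader might also infer that the imbalance rule can never admit the strata. That holds only for a pooled test, and the plan speaks of each site.

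**Conclusion.** The point stands as an improvement to pre-specification. Age group and AF type are absent from every analysis sentence, and the covariates of the deciding models are not fixed. For arrhythmia recurrence, leaving prognostic strata out of a Cox model that already holds Utah stage costs about 0 to 3 points of power and makes the test slightly conservative. The cost is nil if the factors are not prognostic. These sizes rest on assumed stratum hazard ratios, splits and block size. The documents do not support reading this as a threat to validity or as an error in the sample size.

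**What to change.** **Arrhythmia recurrence.** Make the deciding coefficient the treatment effect from one main-effects Cox model. Include age group (under 65, 65 and over) and AF type as randomised, baseline Utah stage coded I-II against III-IV, and the planned physician random effect. Label the log-rank test supportive.

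**Fibrosis.** Add age group and AF type as randomised to the longitudinal model. Do not add two-group Utah stage: it is a coarse band of the outcome's own baseline value, and its effect there has not been examined.

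**Both.** Remove from the primary models the imbalance rule in General Considerations, the unnamed confounders in the recurrence analysis, and the data-dependent confounders in the fibrosis analysis. Report models with further covariates, including those selected for their link with missingness, as sensitivity analyses. Reconcile the age cut-off in Study Design with the two randomisation sections.

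**Cost.** An amendment to wording, best made before outcome data by arm are examined. All variables are already collected and no patients are added.
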